7.3 Vital Signs

Vital sign observed values and change from baseline by parameter (unit) will be summarised over time.

In addition, 'substantial' changes from baseline will be categorised as follows: change from baseline in systolic/diastolic blood pressure (systolic BP [$>\pm 40$ mmHg], diastolic BP [$>\pm 20$ mmHg]) and heart rate ($>\pm 30$ bpm). The number and percentage of subjects with changes from baseline as categorised above will be summarised separately for positive and negative changes over time and at any post-baseline time point.

All vital sign data will be listed including reference ranges flagging all out of range values, change from baseline including flags for substantial changes from baseline.

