## 8. STUDY DESIGN

### 8.1 Primary endpoints

Incidence of adverse events (AE), including Serious adverse events (SAE). AEs will be evaluated between baseline and Follow-up Visit, while SAEs will be evaluated between screening and the last clinic visit or until resolution, whenever possible.

The incidence of abnormal findings in objective assessments (e.g. laboratory values, ECGs, and vital signs) during the course of the study will also be assessed.

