### **10.1.6 Vital Signs**

Vital signs will include the following measures: oral temperature, pulse, systolic and diastolic blood pressure and respiratory rate. Blood pressure and pulse will be determined after the subject has been in the sitting position for 5 minutes.

Blood pressure should be determined by cuff (using the same method, the same arm, and in the same position throughout the study). A BP cuff appropriate for the subject's arm length and girth should be used for all BP measurements. The cuff should be approximately two-thirds the length/width of the subject's arm (from elbow to shoulder). The cuff should be calibrated and ideally the same cuff should be used on a subject throughout the study. All BP measurements should be performed by the same study site personnel (if possible) throughout the study.

Any vital signs which in the opinion of the investigator are deemed to be clinically significant are to be recorded as an AE. Any clinically significant abnormalities at the follow-up visit should be followed up and repeated until they have returned to baseline or are, in the opinion of the investigator, no longer clinically significant.

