### **11.4 Statistical Methods for Safety**

All safety summaries and analyses will be performed using the SAF.

All AEs will be coded using the MedDRA dictionary and will be summarised by treatment using frequencies and percentages as appropriate.

Other safety data, including laboratory, vital signs and ECG values including change from baseline will be summarised. Changes in safety parameters from baseline [REDACTED] over time will be described by treatment dose, and shift tables at time points of interest will be generated. Changes from the start of the [REDACTED] run-in period [REDACTED] to baseline [REDACTED] will also be produced as indicative of the effect of [REDACTED] of [REDACTED] treatment.

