1 INTRODUCTION

This document details the statistical analysis of the data that will be performed for the AMO Pharma Ltd study: A Single-Blind, Phase 2 Study to Evaluate the Safety and Efficacy of Tideglusib 400mg or 1000mg for the Treatment of Adolescent and Adult Congenital and Juvenile-Onset Myotonic Dystrophy.

The proposed analysis is based on the contents of protocol version 4.0 (dated 09-JAN-2017). In the event of future amendments to the protocol, this statistical analysis plan (SAP) may be modified to account for changes relevant to the statistical analysis.

The table, listing and figure shells are supplied in a separate document.

The analysis and statistics reporting will be conducted at [REDACTED] using SAS version 9.2 or higher.

Summary statistics will consist of number of subjects(n), mean, standard deviation (SD), minimum, median and maximum, unless specified otherwise. The precision of these variables is defined in the table, figure and listing shells document.

For categorical variables, the number and percentage of subjects in each category will be presented, based on the number of non-missing observations apart from disposition of subjects, protocol deviations, background and demographic characteristics, prior and concomitant medications and adverse events where the percentage will be based on the number of subjects in the analysis set.

Where mentioned in this SAP, "active treatment" will relate to tideglusib treatment.

Unless otherwise stated, baseline is defined as the last non-missing value (including scheduled and unscheduled assessments) prior to the subject receiving active treatment.

In the final analysis of the combined Cohort 1 and Cohort 2 subject data, data will be summarised in tabular form by the intended dose group according to the cohort (Tideglusib 400mg and Tideglusib 1000mg) apart from disposition of subjects, protocol deviations, and background and demographic data which will be summarised by dose group and overall subjects. In the analysis to be conducted at completion of Cohort 1, the data will be summarised in tabular form for the Tideglusib 1000mg dose group only.

Listings will be sorted by dose group, subject number and time of assessment.

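### SAP 7.3 flags out-of-range vital signs in a listing but does not tabulate how many subjects have them, although their incidence is part of the primary endpoint

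*SAP*

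**What the plan says.** Besides adverse events, the primary endpoint in Protocol 8.1 covers "The incidence of abnormal findings in objective assessments (e.g. laboratory values, ECGs, and vital signs) during the course of the study". Protocol 10.1.6 names five vital signs: "oral temperature, pulse, systolic and diastolic blood pressure and respiratory rate". Protocol 11.4, which deals with laboratory, vital-sign and ECG data together, adds that "shift tables at time points of interest will be generated".

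SAP 7.3 provides the following for vital signs:

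- **Continuous summaries.** "Vital sign observed values and change from baseline by parameter (unit) will be summarised over time". By SAP section 1 these give the number of subjects and "mean, standard deviation (SD), minimum, median and maximum, unless specified otherwise".
- **Counts of large changes.** Three parameters have a threshold for a 'substantial' change from baseline: ±40 mmHg systolic, ±20 mmHg diastolic and ±30 bpm heart rate. For these, "The number and percentage of subjects with changes from baseline as categorised above will be summarised separately for positive and negative changes". The table is to be given by visit and for the post-baseline period as a whole.
- **A listing.** "All vital sign data will be listed including reference ranges flagging all out of range values", with flags for substantial changes.

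SAP 2.5 names one change from the protocol's planned analysis, the biomarker endpoint, and states that there are no others.

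**The concern.** The protocol endpoint asks how many subjects had an abnormal value. The SAP table counts how many moved a long way from their own baseline. These are different events. A subject can leave the reference range after a modest change, or change a great deal and stay inside it. For temperature and respiratory rate nothing is counted.

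The SAP treats the other two assessments named in the endpoint differently. In SAP 7.2, laboratory parameters are classed low, normal or high and get shift tables. In SAP 7.4, ECGs get absolute QT limits and a normal/abnormal tabulation. Only vital signs have no tabulated abnormality.

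If the plan is followed as written, the one vital-sign incidence figure in the report could be taken for the endpoint component when it measures something else. Anyone who wants the stated component must build it from the listing after seeing the data, and must then decide what counts as new and whether unscheduled readings qualify.

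**Working it through.** The documents give no figure to reproduce: there is no sample-size calculation, and neither document prints vital-sign reference limits or expected distributions. The limits, means, SDs and effects below are therefore assumptions. The change thresholds and the 8 subjects per dose group come from the SAP.

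**Step 1. Baseline needed to be counted.** A value that falls to a lower limit L is counted only if baseline B satisfies L − B < −T, so B > L + T. For an upper limit the condition is B < L − T.

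- Heart rate, assumed L = 50, T = 30: baseline above 50 + 30 = 80 bpm.
- Systolic, assumed L = 140, T = 40: baseline below 140 − 40 = 100 mmHg.
- Diastolic, assumed L = 90, T = 20: baseline below 90 − 20 = 70 mmHg.

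Given the limit, this needs no distributional assumption.

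**Step 2. Size over several visits.** Each simulated subject has a true mean, a baseline equal to that mean plus visit noise, and 7 post-baseline readings shifted by a drug effect (200,000 subjects per case). Seven is the number of post-baseline columns in the Schedule of Events: five interim, end of treatment and follow-up. The cells cannot be read, so it is an assumption that vital signs are taken at all seven. A subject is new if out of range at any of these readings but not at baseline.

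| Assumed limit | Mean (SD); visit SD | Effect | Newly out of range | Counted by SAP table | New cases missed |
|---|---|---|---|---|---|
| HR < 50 | 72 (9); 5-7 | −10 bpm | 27-37% | 1-10% | 84-98% |
| SBP > 140 | 118 (11); 7-10 | +15 mmHg | 54-63% | 3-16% | 78-96% |
| DBP > 90 | 72 (8); 5-7 | +10 mmHg | 41-52% | 29-47% | 42-63% |

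In a cohort of 8, the systolic row means 8 × 0.54 to 8 × 0.63, or 4.3 to 5.0 subjects newly high, against 8 × 0.03 to 8 × 0.16, or 0.2 to 1.3 counted.

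The diastolic totals are closer, but they are partly different subjects. With visit SD 5, the table catches 0.41 × (1 − 0.63) = 0.15 of subjects as new cases, so 0.29 − 0.15 = 0.14 are counted without a new high value. With visit SD 7 the figures are 0.52 × (1 − 0.42) = 0.30 and 0.47 − 0.30 = 0.17.

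**Step 3. A different model.** This uses one post-baseline reading, bivariate normal, with within-subject correlation 0.4 to 0.8, a shift of 0 to 15 units towards the limit, and baselines HR 72 (SD 10), SBP 115 (SD 12) and DBP 72 (SD 9). The table misses 77-100% of new HR < 50, 90-100% of new SBP > 140 and 45-100% of new DBP > 90.

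**Step 4. Noise.** With the Step 2 model and no drug effect, about 4-20% of subjects still have a new out-of-range value, depending on the parameter and visit SD. Part of every count in the table above is therefore visit variation.

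**The case against.** The strongest reply is that the information reaches the report by other routes.

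- **Adverse events.** Protocol 10.1.6 and 10.4.6 require clinically significant vital signs to be recorded as adverse events, and SAP 7.1 counts subjects with treatment-emergent events. A reader might infer that abnormal vital signs are counted nowhere. That is wrong: only those not judged clinically significant go untabulated. But Protocol 8.1 lists abnormal objective findings in addition to adverse events, and the judgement is made at a site that knows the treatment (Protocol 9.3).
- **Continuous summaries.** A mean fall of 10 bpm or rise of 15 mmHg would show directly, and the minimum and maximum show extremes. So a drug effect would not be hidden. These summaries still do not say how many subjects were out of range, or whether this was new.
- **ECG.** A reader might infer that bradycardia is the worst-served finding, since the protocol background links adult-onset disease with cardiac conduction block. The documents do not support this. Heart rate is also measured on the ECG (Protocol 10.1.8), and SAP 7.4 summarises ECG values and the normal/abnormal interpretation. Temperature and respiratory rate are the signs with no category. SAP 7.4 does not, however, set a heart-rate limit.
- **Wording.** Protocol 8.1 does not define abnormal, so reading it as out of range is an interpretation, though it is the one SAP 7.2 applies to laboratory values. The synopsis makes shift tables conditional on need, and Protocol 11.4 limits them to time points of interest.
- **Small cohorts.** With 8 subjects per group the count can be made by hand from the listing. That is true, but the definition would then be chosen after the data are seen.

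**Conclusion.** The point holds as a gap in prespecification and reporting of one primary endpoint component. SAP 7.3 gives no number, percentage or shift table for out-of-range vital signs, has no category for two of the five signs, and SAP 2.5 does not declare the omission. No data are lost.

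The substantial-change table cannot stand in for the missing count. Its baseline requirements follow from arithmetic once a limit is chosen. The percentages missed rest entirely on assumed limits, distributions, effects and number of readings, and they differ by parameter: high for heart rate and systolic pressure, moderate for diastolic pressure. It would go too far to conclude that the table would show about zero while many subjects become abnormal. For diastolic pressure it counts 29-47% of subjects under the assumptions used.

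**What to change.** In SAP 7.3 add, by dose group for the Safety Set and for all five vital signs in Protocol 10.1.6:

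1. The number and percentage of subjects with a new value below the reference range, and separately above it, at any post-baseline time, scheduled or unscheduled, where baseline was not already so.
2. A low/normal/high shift table from baseline by visit.

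Use the reference ranges already applied in the listing. State them in the SAP, or cross-refer if they are in the separate shells. Keep the substantial-change counts as supportive.

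The cost is SAP wording and one or two tables, with no new data. Because about 4-20% of subjects may show a new out-of-range value from visit noise alone, add a note that the counts are to be read alongside the continuous summaries.

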7.4 Electrocardiography

Electrocardiography (ECG) observed values and change from baseline will be summarised over time.

The incidence of outliers in absolute QT, QTcF and QTcB intervals (>450 , >480 , and >500 msec), and the change from baseline in QT, QTcF and QTcB intervals (>30 and >60 msec both positive and negative changes) will be summarised over time and at any post-baseline time point.

In addition, the overall interpretation of the ECG (Normal, Abnormal NCS, and Abnormal CS) will also be summarised over time.

All ECG results will be listed including reference ranges flagging all out of range, overall interpretation and change from baseline values.

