## 7. SELECTION AND WITHDRAWAL OF SUBJECTS

### 7.1 Subject numbers

A total of 16 subjects are planned to be enrolled in the study to receive active IMP. Subjects that withdraw during the [REDACTED] run-in phase, will be replaced. Subjects that withdraw from the study after receiving active IMP, will not be replaced.

Subject eligibility will not be re-assessed [REDACTED] run-in period; the run-in period is for the purposes of analysis.

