### 7.3 Exclusion criteria

Subjects are excluded from the study if any of the following exclusion criteria are met:

1. Non-ambulatory (full time) wheel chair user
2. Receiving stimulant medication
3. Receiving other medications/therapies not stable (changed) within 4 weeks prior to Run-in ([REDACTED])
4. Medical illness or other concern which would cause investigator to conclude subjects will not be able to perform the study procedures or assessments or would confound interpretation of data obtained during assessment
5. Current enrolment in a clinical trial of an investigational drug or enrolment in a clinical trial of an investigational drug in the last 6 months
6. Women of child bearing potential who are pregnant, lactating or not willing to use a protocol-defined acceptable\* contraception method if sexually active and not surgically sterile
7. Men, if engaged in sexual relations with a female of child-bearing potential, not using an acceptable\* contraceptive method if not surgically sterile
8. Gastrointestinal disease which may interfere with the absorption, distribution, metabolism or excretion of the study medication and impact the interpretability of the study results
9. Current clinically significant (as determined by the investigator) cardiovascular, renal, hepatic, endocrine or respiratory disease
10. Clinically significant heart disease (in the opinion of the investigator) or second or third degree heart block, atrial flutter, atrial fibrillation, ventricular arrhythmias, or is receiving medication for treatment of a cardiac arrhythmia
11. Average QTcF value of >450msec at [REDACTED]
12. Kidney disease requiring ongoing treatment
13. A history of chronic liver disease with current out of range value for ALT, clinically relevant hepatic steatosis or other clinical manifestations of ongoing liver disease
14. Current ALT value > 2X the upper limit of the normal reference range at [REDACTED] ([REDACTED]) (may repeat to confirm)

15. Current total bilirubin value greater than the upper limit of the normal reference range at [REDACTED] (unless due to Gilbert's syndrome) (may repeat to confirm)
16. HbA1c values greater than 6% or 42.0mmol/mol at [REDACTED] (may repeat to confirm)
17. TSH values outside of the normal reference range at [REDACTED] (may repeat to confirm)
18. Serum creatinine >150 µmol/L and creatinine clearance ≤ 60 mL/m (according to Cockcroft-Gault formula) at [REDACTED] (may repeat to confirm)

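### SAP 7.4 counts absolute QT, QTcF and QTcB values above 450, 480 and 500 msec after baseline without separating those already above the limit before tideglusib

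*SAP*

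**What the plan says.** SAP 7.4 sets two kinds of QT category in one sentence. The absolute rule covers "The incidence of outliers in absolute QT, QTcF and QTcB intervals", with limits of 450, 480 and 500 msec. The change rule covers "the change from baseline in QT, QTcF and QTcB intervals (>30 and >60 msec both positive and negative changes". Both "will be summarised over time and at any post-baseline time point". Neither rule refers to the other, and the absolute rule sets no condition on the baseline value. The section also plans observed values, changes from baseline and the overall ECG interpretation over time, and adds: "All ECG results will be listed including reference ranges flagging all out of range, overall interpretation and change from baseline values". SAP 1 defines baseline as the last available value before active treatment.

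On entry, protocol 7.3 exclusion 11 reads "Average QTcF value of >450msec at", with the visit blacked out. Protocol 10.1.8 says that the triplicate screening ECGs decide eligibility. No exclusion limits QTcB or uncorrected QT. Protocol 7.1 states, in relation to the run-in period, "Subject eligibility will not be re-assessed".

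Protocol 8.1 places "The incidence of abnormal findings in objective assessments" over the course of the study among the primary endpoints and gives ECGs as an example.

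The protocol synopsis names laboratory and ECG values as objective safety assessments to be summarised by treatment period, and then mentions shift tables as required. Protocol 11.4 lists ECG with the other safety data and plans shift tables, together with changes from the start of run-in to baseline. SAP 7.2 provides shift tables for laboratory data. SAP 7.4 provides none for ECG, and no run-in display. SAP 2.5 names one departure from the protocol, a biomarker, and says there are no others.

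**The concern.** Elsewhere the SAP ties its safety categories to the state before treatment: adverse events are split by onset (7.1), laboratory results get shift tables (7.2), and vital-sign categories are changes from baseline (7.3). The absolute QT categories have no such tie. A reader will naturally take a post-baseline outlier rate as a description of what arose after tideglusib was started, but a subject who was above the limit beforehand and did not change is in the same numerator.

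With 8 subjects per dose, one or two such cases change the row visibly. The cohorts are also sequential and not randomised. A cohort with a faster resting heart rate would show more QTcB values above 450 msec with no difference in drug effect. This display serves a component of the primary endpoint, so the table should be readable without going back to listings.

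**Working it through.** The plan states no figure on this point, so there is none to reproduce. The check asks whether an eligible subject can already be in an outlier category at baseline, and how far this reaches.

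**Inputs.** Entry limit QTcF 450 msec (protocol 7.3); thresholds 450, 480 and 500 msec (SAP 7.4); 8 subjects per dose group (SAP 2.4). The individual QTcF and heart-rate values below are illustrative; the documents give no distribution for either.

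**Formulas.** With RR = 60/HR, Bazett is QTcB = QT/RR^(1/2) and Fridericia is QTcF = QT/RR^(1/3). Hence:
- QTcB = QTcF × (HR/60)^(1/6)
- QT = QTcF × (60/HR)^(1/3)

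**The 450 msec threshold.**
- QTcF 440: QTcB exceeds 450 when HR is above 60 × (450/440)^6 = 68.7 bpm. At 75 bpm, QTcB is 456.7.
- QTcF 430: QTcB exceeds 450 when HR is above 60 × (450/430)^6 = 78.8 bpm.
- QTcF 440: uncorrected QT exceeds 450 when HR is below 60 × (440/450)^3 = 56.1 bpm. At 55 bpm, QT is 452.9.

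**The higher thresholds, at the QTcF entry limit of 450.**
- QTcB exceeds 480 only above 60 × (480/450)^6 = 88.4 bpm, and 500 only above 60 × (500/450)^6 = 112.9 bpm.
- QT exceeds 480 only below 60 × (450/480)^3 = 49.4 bpm.

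**Consequence in the table.** A subject with QTcB 456.7 before and after dosing is counted in the >450 row and in no change category. One subject is 1/8 = 12.5 percentage points.

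**How often this might happen.** A simulation with no drug effect gives an order of magnitude. All its inputs are assumptions: mean QTcF 410 to 425 msec (SD 18 between subjects, 8 within), mean heart rate 65 to 75 bpm (SD 10 between, 5 within), screening QTcF at or below 450, a separate baseline ECG, and 4 to 6 post-baseline ECG visits.

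| >450 msec | Counted as written | New only (share of all eligible) | At least one of 8 counted though already above at baseline |
|---|---|---|---|
| QTcB | 11–50% | 7–24% | 29–91% |
| QT | 3–24% | 2–15% | 5–56% |
| QTcF | 3–14% | 2–10% | 5–25% |

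Among subjects counted for QTcB, the share already above 450 at baseline runs from 0.046/0.135 = 34% to 0.254/0.453 = 56% across these settings. With mean QTcF 410 and 4 visits, raising the mean heart rate from 65 to 75 bpm moves the QTcB count from 11.3% to 22.9% with no drug effect. The new-only column is not zero because values also cross the limit by ordinary variation, so a split removes pre-existing cases but not chance crossings.

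**The case against.** The strongest reply is that SAP 7.4 already holds what is needed to resolve each case. It gives change categories, observed values and changes over time, and a complete listing. With about 16 subjects, anyone can see that an unchanged QTcB of 457 was there before. This stands as mitigation: the information is not lost. It does not make the incidence table itself separate the two kinds of case.

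The count also matches the endpoint literally, since protocol 8.1 speaks of abnormal findings during the study and not of newly emergent ones. That is a reason to keep the absolute count and add to it.

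A baseline row may exist. The SAP's wording on summaries over time does not exclude one, and the table shells are a separate document. The absence of a baseline display is therefore not established; what is established is that the SAP text does not require one.

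A reader might infer that the SAP treats these values as events on drug. It does not say so. They become adverse events only if the investigator judges them clinically significant (protocol 10.4.6), and the period after baseline may include the off-treatment follow-up visit. A reader might also infer that all three thresholds are equally affected; the arithmetic above shows that they are not, and the QTcF rows are largely protected by the entry limit. Finally, QTcF is tabulated beside QTcB, and SAP 7.4 plans no formal ECG comparison between doses, which limits the harm from a heart-rate difference between cohorts.

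**Conclusion.** The point holds as a gap in a descriptive safety table. The planned absolute counts mix new and pre-existing values, mainly in the >450 msec row for QTcB and uncorrected QT, and each pre-existing case adds 12.5 percentage points in a group of 8. That an eligible subject can be in this position follows from the entry criteria and the two correction formulas. How often it will occur rests on assumed QT and heart-rate distributions that the documents do not supply, so the simulated ranges are only illustrative.

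The omission of an ECG shift table is a related inconsistency between documents. Protocol 11.4 foresees shift tables for safety parameters in a paragraph that includes ECG, and the SAP neither provides one for ECG nor declares the change. The synopsis qualifier (as required) leaves some latitude, so this is a gap to reconcile and not a clear breach.

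The documents do not support dropping subjects who start above a limit or removing the uncorrected QT rows. A subject going from 452 to 478 msec would then vanish from every category: not counted above 450, below 480, and with a rise of 26 that misses the >30 category. Priority is low to moderate.

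**What to change.** In SAP 7.4:

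1. Keep every planned absolute count, including uncorrected QT, on all subjects in the group.
2. Under each threshold add two rows: *new* (baseline at or below that threshold, with the number of such subjects printed as the denominator) and *already present at baseline*.
3. Show the same categories at the start of run-in and at baseline, where the schedule provides an ECG, so that the reader can see how often limits are crossed before tideglusib.
4. Add a shift table from baseline category to worst post-baseline category for QT, QTcF and QTcB, and state whether the follow-up visit and unscheduled ECGs count.
5. If no ECG shift table is wanted, record that in SAP 2.5 as a change from protocol 11.4.

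The cost is a few sentences, a baseline flag in the program and some extra table rows. The denominators for *new* may fall below 8, so those rows should be read as counts first and percentages second. No planned safety output is lost.
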